3.5.2. Analysis Visit Windows

Subject visits may not occur on protocol-specified days. Therefore, for the purpose of analysis, observations will be assigned to analysis windows for efficacy data in the core studies (Table 3-1 and Table 3-2) and GLPG0634-CL-205 (Table 3-3 and Table 3-4), and for non-efficacy data (Table 3-5). The analysis visit windows for non-efficacy data will be applied up to the last dose date of any study drug.

The baseline value is defined as follows:

Efficacy data:

- Core baseline: The last nonmissing value on or prior to the first dose date of study drug in the core studies
- Extension baseline: The last nonmissing value on or prior to the first dose date of study drug in GLPG0634-CL-205, and no earlier than the core study nominal Week 24 visit date

Safety data:

- Filgotinib baseline: The last nonmissing value on or prior to the first dose date of filgotinib in the core studies or GLPG0634-CL-205

Table 3-1. Analysis Visit Windows for Efficacy Data (SF-36 and FACIT-Fatigue Excluded) in the Core Studies

Analysis Visit	Nominal Study Day	Lower Limit	Upper Limit
Core Baseline	1	(none)	1
Core Week 1	8	2	11
Core Week 2	15	12	22
Core Week 4	29	23	43
Core Week 8	57	44	71
Core Week 12	85	72	99
Core Week 16	113	100	127
Core Week 20	141	128	155
Core Week 24	169	156	≥169

Table 3-2. Analysis Visit Windows for SF-36 and FACIT-Fatigue in the Core Studies

Analysis Visit	Nominal Study Day	Lower Limit	Upper Limit
Core Baseline	1	(none)	1
Core Week 4	29	2	57
Core Week 12	85	58	127
Core Week 24	169	128	≥169

Table 3-3. Analysis Visit Windows for Efficacy Data (SF-36 and FACIT-Fatigue Excluded) in GLPG0634-CL-205

Analysis Visit	Nominal Study Day	Lower Limit	Upper Limit
Extension Baseline	1	(none)	1
Extension Week 12	85	2	127
Extension Week 24	169	128	211
Extension Week 36	253	212	295
Extension Week 48	337	296	379
Extension Week 60	421	380	463
Extension Week 72	505	464	547
Extension Week 84	589	548	631
Extension Week W	7xW+1	7xW-40	7xW+43

Table 3-4. Analysis Visit Windows for SF-36 and FACIT-Fatigue in GLPG0634-CL-205

Analysis Visit	Nominal Study Day	Lower Limit	Upper Limit
Extension Baseline	1	(none)	1
Extension Week 48	337	2	505
Extension Week 96	673	506	841
Extension Week W	7xW+1	7xW-166	7xW+169

Table 3-5. Analysis Visit Windows for Non-Efficacy Data

Analysis Visit	Nominal Study Day	Lower Limit	Upper Limit
Filgotinib Baseline	1	(none)	1
Week 12	85	2	127
Week 24	169	128	211
Week 36	253	212	295
Week 48	337	296	379
Week 60	421	380	463
Week 72	505	464	547
Week 84	589	548	631
Week W	7xW+1	7xW-40	7xW+43

CRP measured on or after nominal follow up visit will not be assigned analysis window and summarized, but will be included in the listing.

Vital signs, ECG, and safety laboratory data collected in the follow up period will also be summarized. The analysis window for the post-treatment follow-up period is defined as from (last dose date of filgotinib + 1 day) to (last dose date of filgotinib + 30 days). If multiple valid, nonmissing measurements exist in the post treatment follow-up visit window, the latest record will be selected for analysis. If the chronological order cannot be determined, for any given subject, the value with the worst severity will be selected for categorical variable, and the average will be taken for continuous variable. Data obtained after last dose date plus 30 days will be excluded from the summaries, but will be included in the listings.

3.5.3. Selection of Non-Efficacy Data in the Event of Multiple Records in an Analysis Visit Window

Depending on the statistical analysis method, single values may be required for each analysis window. For example, change from baseline by visit usually requires a single value, whereas a time-to-event analysis would not require 1 value per analysis window.

If multiple valid, nonmissing, continuous measurements exist in an analysis window, records will be chosen based on the following rules if a single value is needed:

- In general, the filgotinib baseline value will be the last nonmissing value on or prior to the first dose date of filgotinib in the core studies or GLPG0634-CL-205, unless otherwise specified. If multiple measurements occur on the same day, the last nonmissing value prior to the time of first dose of filgotinib in the core studies or GLPG0634-CL-205 will be considered as the filgotinib baseline value. If these multiple measurements occur at the same time or the time is not available, the average of these measurements (for continuous data) will be considered the filgotinib baseline value.
- For postbaseline visits:
 - The record closest to the nominal day for that visit will be selected.
 - If there are 2 records that are equidistant from the nominal day, the later record will be selected.
 - If there is more than 1 record on the selected day, the average will be taken, unless otherwise specified.

If multiple valid, nonmissing, categorical measurements exist in an analysis window, records will be chosen based on the following rules if a single value is needed:

- For filgotinib baseline, the last available record on or prior to the date of the first dose of filgotinib in the core studies or GLPG0634-CL-205 will be selected. If there are multiple records with the same time or no time recorded on the same day, the value with the lowest severity will be selected (eg, normal will be selected over abnormal for safety ECG findings).

- For postbaseline visits:
 - The record closest to the nominal day for that visit will be selected.
 - If there are 2 records that are equidistant from the nominal day, the later record will be selected.
 - If there is more than 1 record on the selected day, the value with the worst severity will be selected (eg, abnormal will be selected over normal for safety ECG findings), unless otherwise specified.

The rules for selecting efficacy data in the event of multiple records in an analysis visit window are specified in Section [6.1](#).

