 - Subjects with persistent abnormal laboratory values associated with the use of the study medication (including but not limited to hematology, liver and renal function values) during one of the 2 core studies (GLPG0634-CL-203 or GLPG0634-CL-204), according to the investigator's clinical judgment.
 - Subjects with diagnosis since the inclusion to GLPG0634-CL-203 or GLPG0634-CL-204 core studies of rheumatic autoimmune disease or inflammatory joint disease other than RA, except for secondary Sjögren's syndrome.
- Primary Endpoint:** Safety and tolerability of long-term dosing of filgotinib 200 mg q.d. and 100 mg b.i.d.

- Secondary Endpoints:** Evolution in the percentage of subjects achieving American College of Rheumatology (ACR)20, ACR50, ACR70, and ACR-N responses; European League Against Rheumatism (EULAR) responses; ACR/EULAR remission, clinical disease activity index (CDAI), simplified disease activity index (SDAI), and the disease-activity score based on 28 joints (DAS28 c-reactive protein [CRP]) every 12 weeks or until the Final Visit or the Early Discontinuation Visit (EDV). Change from Baseline in the Quality of Life (functional assessment of chronic illness therapy [FACIT] fatigue scale and 36-item short form health survey [SF-36] scores) every 48 weeks or until the Final Visit or the EDV.
- Safety Analysis:** The safety analysis will be performed for all subjects who used the study medication at least once in this study. Assessment of treatment-emergent adverse events, and of changes from Baseline in laboratory parameters, vital signs, physical examination, and electrocardiograms.
- Efficacy Analysis:** ACR20, ACR50, ACR70, ACR-N, EULAR response, and ACR/EULAR remission, DAS28(CRP), components of the ACR, and DAS28, CDAI, SDAI, and Quality of Life data (FACIT fatigue scale and SF-36 questionnaire) at each post dosing visit (as appropriate) will be analyzed descriptively. Changes from Baseline will be examined to check for evolution over time in treatment effect.

4 Table of Contents

1	Protocol Approval Signatures	2
2	Study Personnel	3
3	Synopsis	4
4	Table of Contents	7
	LIST OF TABLES	9
5	List of Abbreviations and Definition of Terms	10
6	Introduction	12
6.1	Rheumatoid Arthritis	12
6.2	Background on Filgotinib	13
6.3	Background - Pre-clinical Studies	13
6.3.1	Physical, Chemical and Pharmaceutical Properties and Formulations	13
6.3.2	Nonclinical Pharmacology	14
6.3.2.1	Primary and Secondary Pharmacology	14
6.3.2.2	Safety Pharmacology	14

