8.8.1 Efficacy and Safety Measurements Assessed and Flow Chart

8.8.1.1 Efficacy Assessments

8.8.1.1.1 Evaluation of Disease Activity

Efficacy assessments (excluding FACIT and SF-36) will be carried out at every visit, except the Follow-up Visit. FACIT and SF-36 will be carried out at the AV and the Final Visit/EDV.

Each of 68 joints will be evaluated for tenderness, and each of 66 joints will be evaluated for swelling, except upon receipt of an intra-articular injection of corticosteroid in the previous 3 months, where joints will be classed as not assessable (Appendix 13.2).

A joint assessor with adequate training and experience in performing joint assessments will be designated at each study site to perform all joint assessments. The joint assessor should preferably be a rheumatologist; however, if a rheumatologist is not available, it should be a health care worker with at least one year's experience in performing joint assessments. The assessor should remain the same throughout the study per subject, as much as possible. It is required that the designated joint assessor identify an appropriate back up assessor to provide coverage if the designated joint assessor is absent.

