8.8.1.1.5 FACIT Fatigue Scale

The FACIT fatigue scale (version 4) measures an individual's level of fatigue during their usual daily activities over the past week. It consists of 13 questions with a 7-day recall period on a 5-point Likert scale, with 0 indicating "not at all" and 4 indicating "very much". The total score ranges from 0 to 52. The higher the score, the better the quality of life (Appendix 13.6).

8.8.1.1.6 36-Item Short-form Health Survey (SF-36)

The health-related quality of life of the subject will be assessed using the SF-36 (version 2) with a 4-week recall period. This consists of 36 questions belonging to 8 domains in 2 components:

- Physical well-being: 4 domains: physical functioning (10 items), role physical (4 items), bodily pain (2 items), and general health (GH) perceptions (5 items).
- Mental well-being: 4 domains: vitality (4 items), social functioning (2 items), role emotional (3 items), and mental health (5 items).

The remaining item (health transition) is not part of the above domains but is kept separately (Appendix 13.7).

These scales will be rescaled from 0 to 100 (converting the lowest possible score to 0 and the highest possible score to 100), with higher scores indicating a better quality of life.

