6. EFFICACY ANALYSES

6.1. General Considerations

The primary analysis set for efficacy analyses will be the FAS, defined in Section 3.1.1.

If multiple valid, nonmissing efficacy measurements exist in an analysis window, records will be chosen based on the following rules if a single value is needed:

- The record closest to the nominal day for that visit will be selected
- If there are 2 records that are equidistant from the nominal day, or more than 1 record (with time known) on the selected day, the latest record will be taken
- If chronological order cannot be determined (eg, more than 1 record on the same day with time missing), for any given subject, the worst outcome will be selected.

For the calculation of composite endpoints including DAS28(CRP), ACR20/50/70, ACR-N, SDAI, CDAI and ACR/EULAR remission, we use the following steps unless otherwise specified:

- Step 1: Assign individual components to analysis visit windows defined in Section 3.5.2.
- Step 2: Within each analysis visit window, select the component-level data based on the rules for selecting efficacy data as above
- Step 3: Calculate the composite endpoint based on the selected component-level data in Step 2.

Below are the descriptions for the imputation methods that will be used throughout the efficacy analyses:

- Observed case (OC): Missing values remain missing. For the categorical composite endpoints, in the case that some components are missing, the composite endpoint assessment will be derived based on the non-missing components. If non-missing components are not sufficient to determine final composite endpoint, then the composite endpoint will be set as missing. For continuous composite endpoints (including ACR-N), if any components are missing, the composite endpoints will be set as missing.
- Non-responder imputation (NRI): For all binary response measurements, starting from OC, all missings will be set as non-responders.

If a subject only has core baseline measurements, OC analyses will not include this subject. But this subject will be treated as non-responder in NRI analyses.

For a specific visit if both regular CRP and high-sensitive CRP are available, only regular CRP will be used.

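### The SF-36 and FACIT-Fatigue windows report early-discontinuation values under distant annual labels and leave out many Final Visit/EDV values, because the SAP has no Final Visit/EDV analysis visit for these scales

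*SAP*

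**What the plan says.** **Collection.** Protocol Section 8.8.1.1.1 states: "FACIT and SF-36 will be carried out at the AV and the Final Visit/EDV". Section 8.7.2.2 allows one week either side of the annual visit. The synopsis gives the quality-of-life endpoint as change from Baseline "every 48 weeks or until the Final Visit or the EDV".

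**Windows.** SAP Table 3-4, headed "Analysis Visit Windows for SF-36 and FACIT-Fatigue in GLPG0634-CL-205", has these rows (nominal day, lower limit, upper limit):
- "Extension Week 48 337 2 505"
- "Extension Week 96 673 506 841"
- "Extension Week W 7xW+1 7xW-166 7xW+169"

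Days are counted from the first dose in study 205 (SAP Section 3.5.1).

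**Selection.** When several efficacy records share a window and one value is needed, SAP Section 6.1 says: "The record closest to the nominal day for that visit will be selected". If two are equally distant, the later one is used.

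**Analysis.** SAP Section 6.4 summarises continuous efficacy endpoints as observed cases, by treatment and visit, without formal testing. Section 6.2 takes change from core baseline. Neither these sections nor Section 3.5.2 defines a Final Visit, EDV or last-value time point for the two scales.

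**The concern.** Fatigue and quality of life are a named secondary objective (Protocol Section 7.2, SAP Section 1.1), and these two questionnaires carry most of it. Because the windows are contiguous and the scales are annual, a value collected off the annual schedule has one of two fates: it takes the label of an annual visit that may be far away, or it gives way to the annual record. The off-schedule values are the ones taken when a subject leaves the study.

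The Week 48 column can therefore mix about a year of extension treatment with values taken after days or weeks. For SF-36 there is a further problem. It is assessed "using the SF-36 (version 2) with a 4-week recall period" (Protocol Section 8.8.1.1.6), and Protocol Section 8.7.1.1 provides no gap between core and extension studies. A questionnaire on day 22 thus looks back partly into the core study, where some subjects were on placebo or a lower daily dose (design table, Protocol Section 8.1). FACIT-Fatigue, with its 7-day recall, does not share this problem at day 22.

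In later years, whether a departure value is summarised depends on which half of the 48-week cycle it falls in.

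**Working it through.** **Reproducing the table.** The general row gives nominal 7W+1 and limits 7W−166 to 7W+169.
- W = 96: nominal 673, limits 506 to 841. This matches the table.
- W = 48: nominal 337, limits 170 to 505. The table has 2 to 505, so only the lower limit differs.
- Distance from nominal in the general window: (7W+1) − (7W−166) = 167 days before, and (7W+169) − (7W+1) = 168 days after.
- Distance in the Week 48 window as printed: 337 − 2 = 335 days (47.9 weeks) before, and 505 − 337 = 168 days (24.0 weeks) after. Its length is 505 − 2 + 1 = 504 days.

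**Where a Final Visit or EDV value goes**, with the Week 48 visit, if reached, held on day 337 and non-missing:

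| Final Visit/EDV | Day | Window | Result |
|---|---|---|---|
| Week 3 | 22 | Week 48 | Reported as Week 48, 315 days (45 weeks) early |
| Week 36 | 253 | Week 48 | Reported as Week 48, 84 days (12 weeks) early |
| Week 60 | 421 | Week 48 | 84 days from nominal against 0 for the annual record: not selected |
| Week 72 | 505 | Week 48 | 168 days against 0: not selected |
| Week 72 plus one day | 506 | Week 96 | Reported as Week 96, 167 days (23.9 weeks) early |
| Week 84 | 589 | Week 96 | Reported as Week 96, 84 days (12 weeks) early |

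After an on-schedule Week 48 visit, all 168 days from 338 to 505 lead to omission. The next 167 days, 506 to 672, lead to a Week 96 label ahead of time. The pattern repeats in each cycle; for Week 96 the omitted days are 674 to 841. This is a share of calendar days. It is a share of subjects only if departures are assumed uniform over the cycle, in which case it is about half.

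**Allowing for the visit tolerance.** Take the annual visit on each of the 15 days from nominal −7 to +7, and the Final Visit or EDV 1 to 168 days later: 15 × 168 = 2520 combinations.
- Annual visit k days late: the last k gaps fall in the next window. The sum of k for k = 1 to 7 is 28 (1.1%).
- Annual visit k days early: a later record within 2k days is as close or closer, and the tie rule favours the later one. The sum of 2k for k = 1 to 7 is 56 (2.2%).
- Later record not selected: 2520 − 28 − 56 = 2436 (96.7%).

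These combinations are counted equally; they are not weighted by how often they would occur.

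**Comparison with Table 3-3.** The same style of window there runs from 7W−40 to 7W+43, or 41 days before to 42 days after nominal, because those measures are quarterly. Its first window also starts at day 2, against 44 by formula (7 × 12 − 40), so the largest early label is 85 − 2 = 83 days, compared with 335 in Table 3-4.

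**The case against.** A fair defence has several parts.

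- **Convention.** Starting the first post-baseline window at day 2 is the SAP's practice throughout, and contiguous windows assign every value somewhere. This stands as an explanation. The cost is small for quarterly measures and much larger for annual ones.
- **On-schedule attenders.** A subject with a timely Week 48 questionnaire has that record selected, so the window's width does not alter that subject's Week 48 value. This stands. Mislabelling affects only subjects without a usable record closer to nominal, and their number is unknown.
- **Nothing is destroyed.** Omitted values remain in the data and may appear in the by-subject listings planned in SAP Section 3. If the annual value is missing, the later value is used under the annual label. This stands: the omission is from summaries and plots.
- **Protocol wording.** A reader might infer that the SAP breaches the protocol endpoint. The phrase about the Final Visit or EDV can equally mean how long assessment continues. The synopsis uses similar wording for the 12-weekly measures, and Protocol Section 8.9.1.4 leaves analysis details to the SAP. The documents do not establish a breach.
- **Direction of bias.** A reader might infer that the displayed means look better than the measured data, since treatment failure is a reason to stop (Protocol Section 8.4.2). The documents do not support this. EDV values before Week 48 are counted in the Week 48 column, which would pull the other way if they are poor. The omitted values also include Final Visits of completers, who leave because of approval or reimbursement.
- **Standing of the endpoint.** These are descriptive secondary summaries in an open-label safety study. That limits the weight of the point but does not make the labels correct.

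**Conclusion.** The point holds as a labelling and omission problem in a stated rule. As written, a Final Visit or EDV value can be reported under an annual label up to 335 days (47.9 weeks) ahead in the first window and 167 days (23.9 weeks) ahead in later ones. With an on-schedule, non-missing annual value, any Final Visit or EDV value in the 168 days after the nominal annual day enters no by-visit summary, whether the subject completed or withdrew. Late or early annual visits within the one-week tolerance change this in 84 of 2520 equally counted combinations (3.3%).

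These results rest only on Table 3-4, the selection rule and the collection schedule. No conclusion follows about how many subjects are affected or which way the means move, because that needs departure times and scores that the documents do not give. The change is worth making: the data are already collected and the correction is cheap.

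**What to change.** 1. **Add a Final Visit/EDV analysis visit** for SF-36 and FACIT-Fatigue to SAP Table 3-4 and Section 6.4. Summarise value and change from core baseline, split by completed versus discontinued early, and show time on treatment alongside. This is the essential part, because it is the only step that brings the omitted values into a summary. State whether a record that also falls in an annual window counts in both places.
2. **With that row in place, narrow the annual windows** to values near the annual visit. One option is the Table 3-3 width, 7W−40 to 7W+43: days 296–379 for Week 48 and 632–715 for Week 96. Values on days 2–295 and 380–631 would then carry no annual label.

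The order matters. Narrowing alone would remove early-departure values from the annual columns and show them nowhere. Adding the row alone would cure the omission but leave the misleading labels.

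The cost is a table edit and one extra descriptive summary per instrument, with no new data collection. SAP Section 1 already provides for documenting changes made after finalisation in the study report. There are two downsides, and both should be footnoted. The annual columns will hold fewer observations and will describe subjects still on study near that visit. The Final Visit/EDV row will pool very different treatment durations.

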- Complicated herpes zoster infection (with multi-dermatomal, disseminated, ophthalmic, or CNS involvement)
- Evidence of active HCV during the study, as evidenced by HCV RNA positivity
- Evidence of active HBV during the study, as evidenced by HBV DNA positivity
- Unacceptable toxicity, or toxicity that, in the judgment of the investigator, compromises the subject's ability to continue study-specific procedures or is considered to not be in the subject's best interest

- Treatment failure deemed by the investigator as lack of improvement or worsening of the disease symptoms or occurrence of intolerable AEs.
- Subject request to discontinue for any reason
- Subject noncompliance
- Pregnancy during the study (Section 8.8.1.2.1.5 and Appendix 13.8)
- Discontinuation of the study at the request of Galapagos, a regulatory agency or an institutional review board or independent ethics committee (IRB/IEC)
- Subject use of prohibited concurrent therapy *may* trigger study drug discontinuation; consultation should be made with the *medical monitor*.
- Laboratory criteria:

After becoming aware of any of the below described abnormal laboratory changes occurring at any one time, an unscheduled visit (ie sequential visit) should occur to retest within 3 to 5 days (except for creatinine, which should be retested 7-14 days later, unless medically indicated sooner).

- 2 sequential white cell counts <2000 cells/mm³ (SI: $<2.0 \times 10^9$ cells/L)
- 2 sequential neutrophil counts <1000 neutrophils/mm³ (SI: $<1.0 \times 10^9$ cells/L)
- 2 sequential lymphocyte counts <750 lymphocytes/mm³ (SI: $<0.75 \times 10^9$ cells/L)
- 2 sequential hemoglobin <8.0 g/dL (SI: <80 g/L)
- 2 sequential platelet counts $<75,000$ platelets/mm³ (SI: $<75.0 \times 10^9$ cells/L)
- 2 sequential aspartate aminotransferase (AST) or ALT elevations >3 times the upper limit of normal with at least one total Bilirubin value >2 times the upper limit of normal^a;
- 2 sequential AST or ALT elevations >3 times the upper limit of normal accompanied by symptoms consistent with hepatic injury^a;
- 2 sequential AST or ALT elevations >3 times the upper limit of normal accompanied by elevated INR;
- 2 sequential AST or ALT elevations >5 times the upper limit of normal, regardless of total Bilirubin or accompanying symptoms^a;
- 2 sequential values for estimate creatinine clearance <35 mL/min based on the Cockcroft Gault formula^b;

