8.8.1.3 Flow Chart

Event	Entry Visit	Treatment period ^a			FUV FV + 2 weeks Or EDV + 2 weeks
		D -1 ^c	QEV (q12 weeks)	AV (q48 weeks)	
Study schedule ^b					
Informed consent	X				
Inclusion/ exclusion criteria	X				
Withdrawal criteria		X	X		
Physical examination		X	X	X	X
Pregnancy test ^d	X	X	X	X	X
12-Lead ECG		X	X	X	X
Vital signs ^e		X	X	X	X
TB blood test	X		X		
Clinical laboratory tests ^f		X	X	X	X
IXRS call	X	X	X	X	
Study medication dosing					
Serum CRP		X	X	X	
SJC66		X	X	X	
TJC68		X	X	X	
Physician's global assessment		X	X	X	

Event	Entry Visit	Treatment period ^a			FUV FV + 2 weeks Or EDV + 2 weeks
		D -1 ^c	QEV (q12 weeks)	AV (q48 weeks)	
Study schedule ^b					
Patient's global assessment		X	X	X	
HAQ-D		X	X	X	
FACIT fatigue scale			X	X	
SF-36 questionnaire			X	X	
AE assessment					
Concomitant medications					

- a. During the treatment period, a visit time window of ± 1 week is allowed for each quarterly visit.
- b. QEV=Quarterly Evaluation Visit every 12 weeks; AV=Annual Visit every 48 weeks; FV=Final Visit; EDV=Early Discontinuation Visit; FUV=Follow-Up Visit.
- c. Entry Visit data are those collected at the last visit from the previous core study in which the subject has participated (GLPG0634-CL-203 or GLPG0634-CL-204) for physical examination, 12-lead ECG, vital signs, clinical laboratory tests (including serum CRP and serum pregnancy test), SJC66, TJC68, Physician's Global Assessment, Patient's Global Assessment, HAQ-DI, FACIT fatigue scale, and SF-36 questionnaire, with the exception of demographics, baseline disease characteristics, and medical history.
- d. For female subjects of childbearing potential only. Urine pregnancy test will be performed at Entry Visit and QEV and serum pregnancy test will be performed at AV, Final Visit/EDV and Follow-up Visit. In addition, home urine pregnancy testing will be performed every 4 weeks using home testing kits provided to the subject, as described in Appendix 13.8.
- e. Vital signs are defined as heart rate and blood pressure (systolic and diastolic).
- f. Refer to Section 8.8.1.2.2.

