7.2.1. Summaries of Numeric Laboratory Results

Descriptive statistics of filgotinib baseline values, values at each postbaseline visit and change from filgotinib baseline at each post baseline visit will be provided by treatment group for the following laboratory tests:

- Hematology
 - Hematocrit
 - Hemoglobin
 - Platelet count
 - Red blood cell count
 - White blood cell (WBC) count

- Lymphocytes
- Monocytes
- Neutrophils
- Eosinophils
- Basophils
- Chemistry
 - Alanine aminotransferase (ALT)
 - Aspartate aminotransferase (AST)
 - Alkaline phosphatase (ALP)
 - Total bilirubin
 - Serum creatinine
 - Creatinine clearance by Cockcroft-Gault formula
 - Glucose
- Lipid
 - Triglycerides
 - Total cholesterol
 - HDL
 - LDL
 - LDL/HDL ratio
- Hormone in male subjects
 - Follicle stimulating hormone
 - Inhibin B
 - Luteinizing hormone
 - Testosterone

A filgotinib baseline laboratory value will be defined as the last measurement obtained on or prior to the date/time of first dose of filgotinib in the core studies or GLPG0634-CL-205. Change from filgotinib baseline to a postbaseline visit will be defined as the visit value minus the filgotinib baseline value. The mean, median, Q1, Q3, minimum, and maximum values will be displayed to the reported number of digits; SD values will be displayed to the reported number of digits plus 1.

Median (Q1, Q3) of the observed values for the laboratory tests specified above will be plotted using a line plot by treatment group and visit.

In the case of multiple values in an analysis window, data will be selected for analysis as described in Section 3.5.3.

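### In the by-visit laboratory summaries, a retest can replace the stopping-threshold value that triggered it when the visit was early by at least half the draw-to-retest gap (minor)

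*SAP*

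**What the plan says.** SAP 3.5.2 assigns observations to visit windows, with no exclusion of unscheduled ones. Table 3-5 gives the window for Week W as Day 7W-40 to Day 7W+43, around a nominal Day 7W+1.

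For several continuous non-efficacy records in one window, SAP 3.5.3 says that "records will be chosen based on the following rules if a single value is needed". After baseline the first rule is "The record closest to the nominal day for that visit will be selected". The tie rule is "If there are 2 records that are equidistant from the nominal day, the later record will be selected". Records on the same day are averaged. Neither severity nor scheduled status plays a part.

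SAP 7.2.1 applies this to the numeric laboratory summaries: "In the case of multiple values in an analysis window, data will be selected for analysis as described in Section 3.5.3".

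Protocol 8.4.2 (laboratory criteria) sets the retest: "an unscheduled visit (ie sequential visit) should occur to retest within 3 to 5 days". Creatinine is the exception, "which should be retested 7-14 days later, unless medically indicated sooner". The clock runs from the site's knowledge of the result, not from the draw: "After becoming aware of any of the below described abnormal laboratory changes occurring at any one time". The flow chart in Protocol 8.8.1.3 gives the visit tolerance: plus or minus one "week is allowed for each quarterly visit".

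**The concern.** Under Protocol 8.4.2, what prompts the second draw is the result of the first. A value that meets a stopping threshold brings a second record into its own window, and the closest-to-nominal rule may then prefer that second record. Which value enters the by-visit table therefore depends partly on the outcome.

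If retests tend to be less extreme than the values that triggered them, the by-visit minimum, maximum and change from baseline drift toward normal. Long-term safety is the primary objective, so these tables matter.

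Male hormones deserve most attention. Falls in inhibin B or testosterone with a concurrent FSH or LH rise are stopping criteria in Protocol 8.4.2, and Protocol 6.5 names the testes as a nonclinical target organ. The SAP names hormones only in the by-visit summaries and plots of 7.2.1. The special-interest tables in 7.2.3 cover liver tests and blood counts. The listing in 7.2 names hematology, serum chemistry and urinalysis. The SAP does not say whether CTCAE grading reaches hormones.

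**Working it through.** **1. Do visit and retest share a window?** The Table 3-5 formula reproduces the printed rows. Week 24: 7×24+1 = 169, 168-40 = 128, 168+43 = 211. Week 84: 589, 548, 631. The window thus runs from 41 days before to 42 days after the nominal day. A visit 7 days late, with a 14-day creatinine retest and an assumed 3-day lag, puts the retest 7+14+3 = 24 days after nominal, still inside.

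**2. Condition for replacement.** Let the visit be d days early and the retest be drawn r days after the visit draw. The retest is selected when |r-d| ≤ d, that is, when r ≤ 2d (a tie goes to the later record). For a visit on time or late, the retest is always further from nominal and the triggering value stays.

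**3. Shares.** Assume visit offsets uniform over the 15 whole days from -7 to +7, and no reporting lag.

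| Gap r (days) | Least days early | Offsets where retest is selected | Share |
|---|---|---|---|
| 3 | 2 | 6/15 | 40% |
| 4 | 2 | 6/15 | 40% |
| 5 | 3 | 5/15 | 33% |
| 7 (creatinine) | 4 | 4/15 | 27% |
| 14 (creatinine) | 7 (tie) | 1/15 | 7% |

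Averaged over equally likely gaps:
- 3 to 5 days: (6+6+5)/45 = 17/45 = 38%.
- Creatinine, 7 to 14 days: (4+4+3+3+2+2+1+1)/120 = 20/120 = 17%.

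**4. Reporting lag.** The retest clock starts when the site becomes aware of the result, and Protocol 8.8.1.2.2 sends samples to a central laboratory. The documents give no lag. Assume 3 days:
- Gaps of 6 to 8 days: (5+4+4)/45 = 13/45 = 29%.
- Creatinine gaps of 10 to 17 days: (3+2+2+1+1+0+0+0)/120 = 9/120 = 7.5%.

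**5. Core-study offset.** SAP 3.5.1 counts safety days from the first filgotinib dose, which may be in a core study. If the core Week 24 visit falls on Day 169, the first extension dose is on Day 170, and an on-schedule extension Week 12 visit is on Day 170+84 = 254. The nominal day is 253, so the offsets become -6 to +8. Without lag the shares are (5+5+4)/45 = 14/45 = 31%, and for creatinine 12/120 = 10%.

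**6. Effect on a by-visit mean.** Shift = (share of subjects retested) × (share replaced) × (retest less extreme by how many SD). The documents give neither the first nor the last, so both are assumed, as 0.2% to 2% and 1 to 3 SD:
- Low end: 0.002 × 17/45 × 1 = 0.0008 SD.
- High end: 0.02 × 17/45 × 3 = 0.023 SD.
- Values replaced, if all 739 enrolled subjects have the visit: 739 × 0.002 × 17/45 = 0.6, up to 739 × 0.02 × 17/45 = 5.6.

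**The case against.** The strongest reply is that closest-to-nominal is an explicit, prespecified rule in an open-label, descriptive study, and that the tables built to find abnormalities do not use it. SAP 7.2.2.1 to 7.2.3.2 count any post-baseline value or the worst one, so a retest cannot displace anything there. The plots in 7.2.1 show medians and quartiles, which a few tail values barely move. All of this stands, and it is why the point is minor.

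The entry of unscheduled records into the windows is also an inference. SAP 7.3 mentions unscheduled visits only for baseline selection of weight and vital signs, and 7.2.2.3 summarises categorical laboratory data by scheduled visit. This stands too, but it is a further reason to state the rule.

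A reader might infer more than the documents support:
- **That any early visit loses its value.** A visit one day early never does at a gap of 3 to 5 days, and a 14-day creatinine gap needs a visit a full 7 days early.
- **That safety tables in general are biased.** Protocol 8.4.2 sets no such retest for ECG or vital signs, and analytes such as lipids and glucose have no stopping threshold.
- **That normal values are never replaced.** Unscheduled visits can occur for other reasons, such as a dose change (Protocol 8.1), and nothing limits a repeat sample to the abnormal analyte.
- **That a displaced hormone value leaves no trace.** SAP 7.1.1 codes laboratory adverse events and 7.1.6.1 tabulates those leading to discontinuation. The hormone criterion is also narrow: a 50% fall with a clinically relevant FSH or LH rise, in subjects with normal baseline levels.

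**Conclusion.** The concern holds for the by-visit numeric laboratory summaries in SAP 7.2.1, for analytes with a stopping threshold, and for visits early by at least half the draw-to-retest gap. The replacement shares are conditional on a retest and rest on uniform visit offsets. Reporting lag and the core-study offset both lower them, so the no-lag figures are the upper end of the cases examined.

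The size of any drift cannot be derived from the documents, which give neither a retest rate nor a typical retest result. A retest that confirms the abnormality changes little. Under the assumed inputs the shift in a mean is at most about 0.02 SD. Extremes are more exposed, because one replaced value can change a visit's minimum or maximum. Severity is minor, with male hormones the main reason to act.

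**What to change.** Add a priority order to SAP 3.5.3 for by-visit laboratory summaries:

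1. Select the scheduled quarterly, annual or Final Visit record.
2. Use an Early Discontinuation Visit record only if the window holds none of these.
3. Use an unscheduled record only if the window holds neither.

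The Early Discontinuation Visit must rank below the regular visits. A confirmed abnormality can itself lead to that visit in the same window, and equal rank would bring the outcome-dependent choice back. Closest-to-nominal can still settle ties within a rank. Keep all unscheduled values in the worst-value, graded and threshold tables and in the listings.

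The cost is a short addition to the SAP and a visit-type flag in the derivation. No data are lost, and the abnormality tables do not change.
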